4.2. Scientific Rationale for Study Design

Master Protocol CPMP describes the overall study design rationale.

4.3. Justification for Dose

CCI

4.4. End of Study Definition

A participant is considered to have completed this ISA if they have completed all required phases of the study including the last scheduled procedure shown in the ISA SoA.

The end of the study is defined as the date of the last visit of the last participant in the study or last scheduled procedure shown in the ISA SoA for the last participant.

5. Study Population

Master Protocol CPMP and DPNP DSA CPMP(3) provide eligibility criteria that must be followed for this study. LY3857210-specific inclusion and exclusion criteria are listed here.

5.1. Inclusion Criteria

Participants are eligible to be included in the study only if all of the following criteria apply:

Sex and contraceptive/barrier requirements

[3075] Males and females may participate in this trial.

No male contraception is required except in compliance with specific local government study requirements.

WOCBP and WNOCBP may participate in this trial. See Section 10.4 for definitions and additional requirements related to contraception.

Contraceptive use by participants should be consistent with local regulations regarding the methods of contraception for those participating in clinical studies.

5.2. Exclusion Criteria

Participants are excluded from the study if any of the following criteria apply:

- [3077] Have an eGFR of <30 mL/min/1.73 m , based on the Chronic Kidney Disease Epidemiology Collaboration (CKD-EPI) formula at Visit 1 or Visit 2.
- [3078] Have known allergies to LY3857210, related compounds or any components of the formulation, or history of significant atopy.
- [3079] Women who are pregnant or breastfeeding.

5.3. Lifestyle Considerations

See Master Protocol CPMP for lifestyle considerations.

ISA-specific lifestyle considerations are provided below.

5.3.1. Substance Use

Positive urine drug screen will not be considered illicit use if it is a prescribed concomitant medication for a known preexisting condition.

5.4. Screen Failures

Screen failures are described in Master Protocol CPMP.

5.5. Criteria for Temporarily Delaying Enrollment, Randomization, or Administration of Study Intervention of a Participant

Not applicable to this study.

6. Study Intervention(s) and Concomitant Therapy

6.1. Study Intervention(s) Administered

This table lists the interventions used in this clinical study.

Intervention Name	LY3857210	Placebo			
Dosage Level(s)	45 mg daily	N/A			
Route of Administration	РО	PO			

Abbreviations: N/A = not applicable; PO = by mouth.

Packaging and labeling

Study interventions will be supplied by the sponsor or its designee in accordance with current Good Manufacturing Practice. Study interventions will be labeled as appropriate for country requirements.

6.2. Preparation, Handling, Storage, and Accountability

Preparation, handling, storage, and accountability are described in Master Protocol CPMP.

6.3. Measures to Minimize Bias: Randomization and Blinding

Randomization and blinding are described in Master Protocol CPMP.

6.3.1. Stratification

There are no additional stratification factors for this study.

6.4. Study Intervention Compliance

When participants self-administer study intervention(s) at home, compliance with study intervention will be assessed at each visit. Compliance will be assessed by direct questioning and counting returned capsules and documented in the source documents and CRF. A record of the number of study intervention capsules dispensed to and taken by each participant must be maintained and reconciled with study intervention and compliance records. Intervention start and stop dates will also be recorded in the CRF.

6.5. Dose Modification

Dose modification is not permitted.

6.6. Continued Access to Study Intervention after the End of the Study

Not applicable.

6.7. Treatment of Overdose

In case of suspected overdose, participants should be monitored for any signs or symptoms of adverse reactions or effects, and supportive care should be provided as necessary. There is no known antidote to LY3857210 therapy.

6.8. Concomitant Therapy

6.8.1. Permitted Medications

All concomitant therapies that are part of routine care for comorbidities other than chronic pain are allowed and may be used during the study, except as indicated in Section 6.8.2.

Master Protocol CPMP provides more detail on concomitant therapy.

6.8.2. Prohibited Medications

A list of medications that are prohibited from Visit 2 to Visit 801 for participants randomly assigned to this ISA study will be provided in the Manual of Operations. Participants may return to their routine care after Visit 801 is completed, as clinically appropriate.

Potential drug-drug interactions with LY3857210

Please refer to Section 5.2, IB, and Manual of Operations for details on concomitant medication restrictions.

7. Discontinuation of Study Intervention and Participant Discontinuation/Withdrawal

7.1. Discontinuation of Study Intervention

Master Protocol CPMP and CPMP(3) DSA provide the reasons and procedures for discontinuation of intervention and participant discontinuation that must be followed for this study.

7.1.1. Liver Chemistry Stopping Criteria

Interrupting study intervention based on elevated liver tests

The study intervention should be **interrupted** and close hepatic monitoring initiated (see Section 8.2.5 of Master Protocol CPMP) if 1 or more of these conditions occur:

Elevation	Exception
ALT or AST >8x ULN	•
ALT or AST >5x ULN for more than 2 weeks	
ALT or AST >3x ULN and either TBL >2x ULN or INR >1.5	For participants with Gilbert's syndrome: If baseline direct bilirubin is >0.5 mg/dL, then doubling of direct bilirubin should be used for drug interruption decisions rather than TBL>2x ULN
ALT or AST >3x ULN with the appearance of fatigue, nausea, vomiting, right upper quadrant pain or tenderness, fever, rash,	
and/or eosinophilia (>5%)	
ALP >3x ULN, when the source of increased ALP is the liver	
ALP >2.5x ULN and TBL > 2x ULN	For participants with Gilbert's syndrome: If baseline direct bilirubin is >0.5 mg/dL, then doubling of direct bilirubin should be used for drug interruption decisions rather than TBL>2x ULN
ALP >2.5x ULN with the appearance of fatigue, nausea,	
vomiting, right upper quadrant pain or tenderness, fever, rash, and/or eosinophilia (>5%)	
Source: FDA 2009 and other consensus guidelines, with minor mo	difications.

Abbreviations: ALP = alkaline phosphatase; ALT = alanine aminotransferase; AST = aspartate aminotransferase; INR = international normalized ratio; TBL = total bilirubin level; ULN = upper limit of normal.

Resuming study intervention after elevated liver tests

Resumption of the study intervention can be considered only in consultation with the Lilly-designated medical monitor and only if the liver test results return to baseline and if a self-limited, non-drug etiology is identified. Otherwise, the study intervention should be discontinued.

7.1.2. Hypersensitivity

If the investigator determines that a systemic hypersensitivity reaction has occurred related to study intervention administration, the participant may be permanently discontinued from the study intervention, and the sponsor's designated medical monitor should be notified. If the investigator is uncertain about whether a systemic hypersensitivity reaction has occurred and whether discontinuation of study intervention is warranted, the investigator may consult the sponsor.

For laboratory samples to be obtained at the time of a systemic hypersensitivity event, see Section 10.2.1.

7.2. Participant Discontinuation/Withdrawal from the Study

See Master Protocol CPMP.

7.3. Lost to Follow-Up

See Master Protocol CPMP.

8. Study Assessments and Procedures

Study procedures and their timing are summarized in Master Protocol CPMP, DPNP CPMP(3) DSA, and ISA NP05 SoAs.

LY3857210-specific assessments and procedures are described here.

8.1. Efficacy Assessments

Planned time points for all efficacy assessments are provided in the SoAs.

See Master Protocol CPMP and DSA CPMP(3) for additional information on efficacy assessments.

8.2. Safety Assessments

Planned time points for all efficacy assessments are provided in the SoAs.

See Master Protocol CPMP and DSA CPMP(3) for additional information on safety assessments. Additional Study NP05-specific assessment information is provided below.

8.2.1. Physical Examinations

Complete physical examination, including targeted examination specified below, should be performed at V3 and Visit 801 or ED. Targeted physical examinations of skin, gastrointestinal tract, mammary gland in males, and lymph nodes will also be performed at Visits V5 and V7 as described in the SoA. Any clinically significant abnormal physical examination findings will be reported as AEs.

In addition, a directed neurological assessment will be performed by the investigator (or designee) at the time points specified in the SoA. If abnormalities are noted at these time points, additional examinations should be performed as clinically necessary. The examiner should be familiar with the participant's baseline examination.

Elements of the neurological assessment include inspection for tremor, extraocular movements, brachial and patellar deep tendon reflexes, finger-nose pointing, and Romberg sign.

8.2.2. Electrocardiograms

Single 12-lead ECG will be obtained as outlined in the SoA (see Section 1.3) using an ECG machine that automatically calculates the heart rate and measures PR, RR, QRS, QT, and QTcF intervals. Refer to Section 7.1 of Master Protocol CPMP for QTcF withdrawal criteria and any additional QTcF readings that may be necessary.

Additional details related to ECG are provided in Master Protocol CPMP.

8.2.3. Clinical Safety Laboratory Tests

See NP05 Section 10.2 (Appendix 2) for the list of clinical laboratory tests to be performed and to the SoA for the timing and frequency for ISA NP05.

Additional details are provided in the Master Protocol CPMP.

8.3. Adverse Events, Serious Adverse Events, and Product Complaints

The definitions of the following events can be found in Appendix 3 of Master Protocol CPMP:

- AEs
- SAEs, and
- PCs.

See Master Protocol CPMP Section 8.3 for additional details.

8.3.1. Pregnancy

Collection of pregnancy information

Male participants with partners who become pregnant

- The investigator will attempt to collect pregnancy information on any male participant's female partner who becomes pregnant while the male participant is in this study. This applies only to male participants who receive study intervention.
- After learning of a pregnancy in the female partner of a study participant, the investigator
 - will obtain a consent to release information from the pregnant female partner directly, and
 - o within 24 hours after obtaining this consent will record pregnancy information on the appropriate form and submit it to the sponsor.

The female partner will also be followed to determine the outcome of the pregnancy. Information on the status of the mother and child will be forwarded to the sponsor. Generally, the follow-up will be no longer than 6 to 8 weeks following the estimated delivery date. Any termination of the pregnancy will be reported regardless of gestational age, fetal status (presence or absence of anomalies), or indication for the procedure.

Female participants who become pregnant

• The investigator will collect pregnancy information on any female participant who becomes pregnant while participating in this study. The initial information will be recorded on the appropriate form and submitted to the sponsor within 24 hours of learning of a participant's pregnancy.

- The participant will be followed to determine the outcome of the pregnancy. The investigator will collect follow-up information on the participant and the neonate, and the information will be forwarded to the sponsor. Generally, follow-up will not be required for longer than 6 to 8 weeks beyond the estimated delivery date. Any termination of pregnancy will be reported, regardless of gestational age, fetal status (presence or absence of anomalies), or indication for the procedure.
- While pregnancy itself is not considered to be an AE or SAE, any pregnancy complication or elective termination of a pregnancy for medical reasons will be reported as an AE or SAE.
- A spontaneous abortion, occurring at <20 weeks gestational age, or still birth, occurring at ≥20 weeks gestational age, is always considered to be an SAE and will be reported as such.
- Any post-study pregnancy-related SAE considered reasonably related to the study intervention by the investigator will be reported to the sponsor as described in Master Protocol Section 8.3.1. While the investigator is not obligated to actively seek this information in former study participants, they may learn of an SAE through spontaneous reporting.
- Any female participant who becomes pregnant while participating in the study will discontinue study intervention and continue directly to the follow-up phase.
 The follow-up on the pregnancy outcome should continue independent of intervention or study discontinuation.

8.3.2. Hypersensitivity Reactions

Many drugs, including oral agents and biologic agents, carry the risk of systemic hypersensitivity reactions. If such a reaction occurs, additional data should be provided to the sponsor in the designated CRFs.

Sites should have appropriately trained medical staff and appropriate medical equipment available when study participants are receiving study intervention. It is recommended that participants who experience a systemic hypersensitivity reaction be treated per national and international guidelines.

In the case of a suspected systemic hypersensitivity event, additional blood samples should be collected as described in Section 10.2.1. Laboratory results are provided to the sponsor via the central laboratory.

8.3.3. Adverse Events of Special Interest

Convulsion is an AE of special interest for LY3857210 and will be subject to enhanced surveillance activities. Additionally, convulsion will be analyzed for presentation in the Clinical Study Report in accordance with the SAP.

If a seizure or convulsion is reported, then contact the medical monitor as soon as possible. Additional evaluation or follow-up may be requested.

8.4. Pharmacokinetics

Blood samples will be collected for measurement of plasma concentrations of LY3857210 as specified in the SoA

A maximum of 3 samples may be collected at additional time points during the study if warranted and agreed upon between the investigator and the sponsor. The timing of PK samples may be altered during the course of the study based on newly available data to ensure appropriate data collection.

Instructions for the collection and handling of PK samples will be provided by the sponsor.

The date and time (24-hour clock time) will be recorded for

- LY3857210 administration prior to the PK sample collection, and
- PK sample collection.

PK samples may also be used to evaluate safety or efficacy measures related to concerns arising during or after the study

8.5. Pharmacodynamics

Pharmacodynamic assessments will not be evaluated in this study.

9. Statistical Considerations

Master Protocol CPMP and DPNP DSA CPMP(3) provide statistical considerations. LY3857210-specific considerations are described here.

9.1. Statistical Hypotheses

Master Protocol CPMP describes the primary hypothesis. CCI

9.2. Analyses Sets

The populations are defined in Master Protocol CPMP.

The PK population includes all randomly assigned participants who received a dose of LY3857210 and have at least 1 evaluable PK sample collected.

9.3. Statistical Analyses

If the primary analysis approach needs to be changed, the updated approach will be provided in the SAP and should not lead to modification of this protocol. Any other change to the data analysis methods described, and the justification for making the change, will be described in the SAP and the clinical study report. Additional exploratory analyses of the data will be conducted as deemed appropriate.

The ISA SAP will be finalized prior to unblinding, and it will include more technical and detailed descriptions of the statistical analyses described in this section.

9.3.1. General Considerations

The primary and secondary endpoint and analyses have been described in Master Protocol CPMP.

Any borrowing of placebo or treatment effect information will be specified in the ISA SAP. Secondary and tertiary or exploratory endpoints and analyses are described in Master Protocol CPMP and DPNP DSA CPMP(3).

Handling of missing, unused, and spurious data is addressed prospectively in the overall statistical methods described in the protocol and in the SAP, where appropriate. Adjustments to the planned analyses are described in the final CSR.

9.3.2. Tertiary Analysis

Exploratory analyses may be described in the ISA SAP.

9.3.3. Safety Analyses

Safety analyses have been described in Master Protocol CPMP. Additional ISA-specific safety analyses may be described in the ISA SAP.

[figure not shown]
9.3.4. Exploratory Pharmacokinetic Analyses

Plasma concentrations for LY3857210 will be reported graphically and descriptively. Model-based PK and exposure-response relationships for various efficacy and safety measures may be conducted.

9.4. Interim Analysis

An interim analysis may be conducted for internal decision making. The potential reasons for interim analyses could include futility analyses, early efficacy analyses, safety analyses, PK analyses, or other analyses needed for key business decisions and planning. Unblinding details would be specified in the unblinding plan section of the SAP or in a separate unblinding document. The SAP will describe any interim analyses in greater detail should they occur.

9.5. Sample Size Determination

If there is no treatment

difference between placebo and LY3857210, the probability of meeting the primary objective specified above (that is, false positive) is approximately 0.059.

10. Supporting Documentation and Operational Considerations

10.1. Appendix 1: Regulatory, Ethical, and Study Oversight Considerations

See Master Protocol CPMP for regulatory, ethical, and study oversight considerations.

10.2. Appendix 2: Clinical Laboratory Tests

Master Protocol CPMP describes tests that may be performed at additional times noted in the SoA for this ISA. This table describes tests unique for ISA NP05.

10.2.1. Laboratory Samples to be Obtained at the Time of a Systemic Hypersensitivity Event

Purpose of collecting samples after a systemic hypersensitivity event

The samples listed in this appendix are not collected for acute study participant management. The sponsor will use the laboratory tests results from these samples to characterize hypersensitivity events across the clinical development program.

When to collect samples after a systemic hypersensitivity event occurs

Collect the samples listed below if a systemic hypersensitivity event is suspected. The timing should be as designated in the table, assuming the participant has been stabilized.

Obtain follow-up predose samples at the next regularly scheduled laboratory sample collection (ideally prior to the next dose after the event) to assess post-event return-to-baseline values.

Timing	Laboratory Test ^a
Collect from 30 minutes to 4 hours after the start of	total tryptase
the event.	complements (C3, C3a, and C5a)
• Note: The optimal collection time is from 1 to 2	cytokine panel (IL-6, IL-1β, IL-10, or any cytokine
hours after the start of event.	panel that includes these 3 cytokines)

Abbreviation: IL = interleukin.

a All samples for hypersensitivity testing will be assayed by Lilly-designated laboratory. Results will not be provided to the study site. If samples are not collected or are collected outside the specified time period, this will not be considered a protocol deviation.

What information to record

Record the date and time when the samples are collected.

Allowed additional testing for participant management

The investigator may perform additional tests locally, if clinically indicated, for acute study participant management.

10.3. Appendix 3: Adverse Events and Serious Adverse Events: Definitions and Procedures for Recording, Evaluating, Follow-up, and Reporting

See Master Protocol Appendix 3 for information related to AE and SAE.

10.4. Appendix 4: Contraceptive and Barrier Guidance

10.4.1. Definitions

Word/Phrase	Definition
Women of childbearing potential (WOCBP)	Adult females are considered WOCBP unless they are WNOCBP.
	Females are considered WNOCBP if they
Women not of childbearing potential (WNOCBP)	 have a congenital anomaly such as Müllerian agenesis are infertile due to surgical sterilization, or are postmenopausal.
	Examples of surgical sterilization include total hysterectomy, bilateral salpingo-oophorectomy, bilateral salpingectomy, or bilateral oophorectomy.
	The postmenopausal state is defined as a woman:
Postmenopausal state	 at any age at least 6 weeks post-surgical bilateral oophorectomy with or without hysterectomy, confirmed by operative note; or aged at least 40 years and up to 55 years with an intact uterus, not on hormone therapy^a, who has had cessation of menses for at least 12 consecutive months without an alternative medical cause, AND with a follicle-stimulating hormone >40 mIU/mL; or 55 years or older not on hormone therapy, who has had at least 12 months of spontaneous amenorrhea, or aged at least 55 years with a diagnosis of menopause prior to starting hormone replacement therapy.
	^a Women should not be taking medications during amenorrhea such as oral contraceptives, hormones, gonadotropin-releasing hormone, antiestrogens, Selective estrogen receptor modulators (SERMs), or chemotherapy that could induce transient amenorrhea.

10.4.2. Contraception Guidance

WOCBP who are completely abstinent as their preferred and usual lifestyle, or in a same-sex relationship as their preferred and usual lifestyle:

Must	Must not
agree to either remain abstinent or stay in a same-sex relationship without sexual relationships with males	 use periodic abstinence methods calendar ovulation symptothermal, or post-ovulation declare abstinence just for the duration of a trial, or use the withdrawal method

WOCBP who are NOT completely abstinent as their preferred and usual lifestyle, or NOT in a same-sex relationship as their preferred and usual lifestyle, must do the following:

Topic	Condition
Pregnancy testing	Have a negative serum test result at screening followed by a negative urine result within 24 hours prior to treatment exposure. See the Master Protocol CPMP and the NP05 Schedule of Activities for subsequent pregnancy testing requirements.
Contraception	Agree to use 1 highly effective method of contraception, or a combination of 2 effective methods of contraception.
	These forms of contraception must be used for the duration of the study.

Examples of different forms of contraception:

Methods	Examples
Highly effective contraception (less than 1% failure rate)	 female sterilization combination oral contraceptive pill progestin-only contraceptive pill (mini-pill) implanted contraceptives injectable contraceptives contraceptive patch (only women <198 pounds or 90 kg) total abstinence vasectomy (if only sexual partner) fallopian tube implants (if confirmed by hysterosalpingogram) combined contraceptive vaginal ring, or intrauterine devices
Effective contraception	 male or female condoms with spermicide diaphragms with spermicide or cervical sponges barrier method with use of a spermicide condom with spermicide diaphragm with spermicide, or female condom with spermicide
Ineffective forms of contraception whether used alone or in any combination	 spermicide alone periodic abstinence fertility awareness (calendar method, temperature method, cervical mucus, or symptothermal) withdrawal postcoital douche, or lactational amenorrhea

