2.3.1. Risk Assessment

Study intervention

Toxicology studies and NOAEL exposure

Based on the observed convulsion in the 3-month dog toxicology study (reported in 1 dog) as well as convulsion noted in the rat in vivo micronucleus study (reported in 1 rat), a 10-fold

exposure multiple based on the observed AUC and C_{max} associated with the NOEL for convulsions in dog (the most sensitive species) will be maintained in this study

In addition, neurological examination will be conducted at regular intervals during the study period and AEs related to CNS signs and symptoms will be collected during the study. Participants with a history of seizures will be excluded from the study.

Potential drug-drug interactions

Clinical drug-drug interaction studies have not been conducted with LY3857210. Based on current in vitro data, LY3857210 is a potential inducer of CYP3A4, CYP1A2, CYP2B6, and CYP2C8. To mitigate risk, participants taking sensitive substrates with a narrow therapeutic index are excluded. See Section 5.2 for exclusion criteria and refer to IB for more information.

Information on AEs expected to be related to the study intervention may be found in the IB . Information on SAEs that are expected in the study population independent of drug exposure will be assessed by the sponsor in aggregate, periodically during the course of the study, and may be found in the IB.

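### The contraception appendix accepts six hormonal methods alone with no enzyme-induction condition, although the drug is a potential CYP3A4 inducer with no clinical interaction study: a small gap, cheap to close

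*Protocol*

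**What the plan says.** Protocol Section 5.1 opens the trial to these women: "WOCBP and WNOCBP may participate in this trial". For the contraception rules it points to the appendix: "See Section 10.4 for definitions and additional requirements related to contraception". It adds that "Contraceptive use by participants should be consistent with local regulations".

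Section 10.4.2 applies to WOCBP who are not abstinent, or in a same-sex relationship, as their usual lifestyle. One method from the tier headed "Highly effective contraception (less than 1% failure rate" is sufficient; otherwise two methods from the lower, barrier-type tier are needed. The top tier includes combination and progestin-only pills, implants, injectables, the patch and the combined vaginal ring.

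Section 2.3.1 says "Clinical drug-drug interaction studies have not been conducted with LY3857210" and, from in vitro work, that "LY3857210 is a potential inducer of CYP3A4, CYP1A2, CYP2B6, and CYP2C8". The mitigation it names is that "participants taking sensitive substrates with a narrow therapeutic index are excluded", followed by "See Section 5.2 for exclusion criteria and refer to IB for more information". Section 6.8.2 refers to the same two places and to the Manual of Operations for restrictions on concomitant medication.

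**The concern.** The two sections do not connect. One names induction of CYP3A4 as an open risk. The other rates six hormonal methods as failing less than 1% of the time and accepts each alone, without asking whether the study drug could change that rate.

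The link between the two is general pharmacology, not something the documents state: contraceptive hormones are taken to be cleared partly by CYP3A4. On that assumption, the visible text gives no support for the failure-rate label in a woman taking LY3857210.

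What is at stake is avoidable fetal exposure to an investigational drug. The point does not touch the power, the error rate or the validity of the efficacy comparison.

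**Working it through.** The plan has no figure of its own to reproduce on this point. The check is a reading of the sections side by side, then a rough size.

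**1. What a site would do.** Section 5.1 sends the site to Section 10.4, and 10.4.2 sets the rule. A woman whose only method is a pill satisfies it.

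**2. Count of the top tier.** There are 11 examples.
- Hormonal, 6: combination pill, mini-pill, implant, injectable, patch, combined ring.
- Others, 5: female sterilization, total abstinence, vasectomy, fallopian tube implants, intrauterine devices (hormonal or copper not specified).

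Conditions on particular methods do appear in this tier: a body-weight limit for the patch, a sole-partner condition for vasectomy, and imaging confirmation for tubal implants. Conditions on induction or an added barrier: none. So this is where a site would look for such a condition.

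**3. Against Section 2.3.1.** The named mitigation is the exclusion for sensitive, narrow-index substrates. It does not name contraceptives, and 10.4.2 expressly accepts them. The Section 5.1 sentence on local regulations does not address interaction with the study drug.

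**4. What cannot be read.** Section 5.2 shows criteria 3077 to 3079, but the amendment table cites a criterion 3085, so further criteria exist. Two cases follow.
- No restriction exists elsewhere: hormonal methods are accepted alone and the induction question is left open.
- A restriction exists elsewhere: 10.4.2 accepts alone what another text limits, with no cross-reference.

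Unless the sponsor has grounds that induction does not matter at 45 mg, 10.4.2 needs wording in either case.

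**5. Size.** From the documents: up to about 125 participants, 8 weeks of dosing, and the 1% limit. Assumed: WOCBP are 5% to 15% of participants; 20% to 60% of them use a hormonal method alone; allocation is between 1:1 and 2:1; the 1% is per year; induction multiplies the failure rate by k, from 1 (no effect) to 10.

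| Step | Low | High |
|---|---|---|
| WOCBP | 125 × 0.05 = 6.25 | 125 × 0.15 = 18.75 |
| Hormonal method alone, both arms | 6.25 × 0.20 = 1.25 | 18.75 × 0.60 = 11.25 |
| Of these on LY3857210 | 1.25 × 1/2 = 0.625 | 11.25 × 2/3 = 7.5 |
| Woman-years on drug | 0.625 × 8/52 = 0.096 | 7.5 × 8/52 = 1.154 |
| Expected pregnancies at 1% per year | 0.00096 | 0.0115 |

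Added pregnancies = (k − 1) × the last row.
- k = 1: 0.
- k = 2, low end: 1 × 0.00096 = 0.001.
- k = 10, high end: 9 × 0.0115 = 0.104.

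The range is therefore 0 to about 0.10. The upper end needs the top of every assumed range at once.

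**The case against.** The strongest reply is that the deciding text is not in view. Section 2.3.1 says that people with a seizure history and those on narrow-index substrates are excluded, yet neither criterion appears in the visible part of Section 5.2. Eligibility text related to interactions is therefore missing from this copy, and redacted text is not missing from the plan. The IB, the Manual of Operations and the Master Protocol are not supplied either. This stands as a limit: the gap is shown for 10.4.2 only. It does not remove the point, because 10.4.2 can be read and does not refer to any such restriction.

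Second, the signal is in vitro, the dose justification is redacted, and the role of CYP3A4 in hormone clearance is an outside assumption. This stands too. A reader might infer that LY3857210 makes hormonal contraception fail, or that the plan as a whole leaves the interaction unmanaged. The documents support neither: the first is not shown at this dose, and the second would need the unseen text.

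Third, the six methods may differ in sensitivity to induction (injectables, for example), so one rule for all may be too broad. This is accepted and is met by exempting methods by name.

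Fourth, there are real safeguards: a negative serum test at screening, a negative urine test within 24 hours before dosing, urine tests at Visits 3 to 7 and at early discontinuation, and stopping study drug on pregnancy. They keep out women already pregnant and shorten exposure, but they do not prevent a conception during treatment. The visible documents identify no specific fetal hazard, which keeps the point modest.

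**Conclusion.** The point holds as a cheap, precautionary improvement for patient safety. Section 10.4.2, as it can be read, accepts six hormonal methods alone while Section 2.3.1 leaves CYP3A4 induction clinically untested.

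The size is small: about 1 to 11 women in both arms, about 1 to 8 of them on drug, and 0 to about 0.10 added expected pregnancies. Every step beyond the 125 participants, the 8 weeks and the 1% limit is assumed. The conclusion also rests on contraceptive hormones being partly cleared by CYP3A4.

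Confidence is medium. If the sponsor holds data that induction is irrelevant at 45 mg daily, only a reference is needed. If a restriction already exists elsewhere, the remaining problem is agreement between texts.

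**What to change.** Add a default rule to Section 10.4.2, for both arms because treatment is blinded, from first dose through Visit 801. A WOCBP relying on the combination pill, mini-pill, implant, injectable, patch or combined ring must do one of the following:
- add one barrier method from the lower tier;
- use a listed non-hormonal option (female sterilization, total abstinence, vasectomy, fallopian tube implants) or an intrauterine device;
- use two methods from the lower tier, as already allowed.

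Exempt a method by name where the sponsor has data or exposure-based reasoning that induction at 45 mg daily does not affect it, and give the reference in Section 2.3.1. If Section 5.2, the IB or the Manual of Operations already restricts hormonal methods, align 10.4.2 with that text and refer to it. Match the consent wording.

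Cost: one wording amendment with ethics review, possibly regulatory review, and consent text. The added burden falls on about 1 to 11 women (assumed range) and may prove unnecessary. No new visit, test or procedure is needed, and sample size and error rates are unaffected.
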